1.0 Introduction and Background

1.1 Ovarian Cancer

Ovarian cancer is the twelfth leading cause of cancer death in the United States.¹ Less than 15% of patients are diagnosed at the local stage; for 61%, the cancer has metastasized.¹ For these patients, 5-year survival rates are a dismal 27%.¹

1.2 Cytoreductive Surgery

The standard treatment for women presenting with advanced-stage ovarian cancer is surgical cytoreduction (CRS) and platinum-based chemotherapy agents.² CRS is either performed initially or after the administration of IV chemotherapy in the neoadjuvant (NAC) setting. Primary CRS and NAC followed by CRS have been associated with similar survival outcomes. There are fewer peri-operative complications and an improved quality of life (QOL) with the NAC approach. The standard first line chemotherapy agents, either after CRS or in the NAC setting, are platinum doublet regimens consisting of cisplatin and carboplatin with paclitaxel or docetaxel.² Intraperitoneal (IP) chemotherapy has been associated with improved survival in three randomized controlled trials compared to IV chemotherapy after primary CRS. However, IP chemotherapy has not been widely prescribed in the United States at least in part due to its increased toxicity and poorer QOL. Although the response rate for these first-line therapies is 70-80%, the majority of patients with advanced ovarian cancer will exhibit progression of their disease.²

1.3 HIPEC

Hyperthermic intraperitoneal chemotherapy (HIPEC) is based on the rationale that intraperitoneal chemotherapy has a substantial pharmacokinetic advantage over systemic chemotherapy. The hyperthermia effects cell membranes, cytoskeletons, synthesis of macromolecules and DNA repair mechanisms.³⁻⁴ Furthermore, mild hyperthermia has been shown to potentiate the anti-tumor effects of oxaliplatin, mitomycin C (MMC), and cisplatin.⁵⁻⁹ While hyperthermia has some cytostatic properties, it is the synergistic effect on chemotherapeutic agents which has lead most centers to utilize hyperthermia with chemoperfusion. The primary objective of HIPEC is to maximize drug-tumor interaction while minimizing systemic toxicity. The HIPEC is delivered at the time of CRS and is a single treatment. This single dose treatment offers significant advantages over conventional IP chemotherapy in the decrease in the number of cycles/treatment time and recovery time after each IP dose are avoided.

The timing of peritoneal perfusion is critically important. Extensive evidence shows that the effect of postoperative versus intraoperative peritoneal perfusion is reduced by the rapid formation of intra-abdominal adhesions as well as complications related to intra-abdominal catheters.⁹⁻¹¹ Intraoperative peritoneal perfusion not only allows for the instillation of chemotherapeutic agents in an adhesion-free environment, it also minimizes the number of viable exfoliated tumor cells after resection.¹²⁻¹⁴ Taken together, this represents the biologic foundation for the current use of HIPEC in the treatment of advanced ovarian malignancies.

A Phase II Trial Evaluating Quality of Life After HIPEC in Patients with Stage IIIC and IV Ovarian, Fallopian Tube or Primary Peritoneal Carcinoma
Wake Forest Baptist Comprehensive Cancer Center (WFBCCC)
CCCWFU 83216

1.4 Quality of Life

QOL in individuals receiving CRS plus IP chemotherapy tends to be low. Reports of QOL a year after HIPEC have been reported to return to near baseline levels. However, there is a lack of prospective studies adequately assessing QOL with CRS plus HIPEC in the area of ovarian cancer.

2.0 Objectives

2.1 Primary Objective(s)

- 2.1.1 To compare the QOL in patients with advanced ovarian cancer treated with SOC NAC followed by CRS with HIPEC at 6 weeks post-treatment vs. QOL in patients treated with intravenous-therapy (IV) chemotherapy presented in Armstrong et al. (2006).

2.2 Secondary Objective(s)

- 2.2.1 To describe the QOL in patients with advanced ovarian cancer treated with NAC followed by CRS with HIPEC at 3 and 6 months post-treatment.
- 2.2.2 To describe neurotoxicity in patients with advanced ovarian cancer treated with NAC followed by CRS with HIPEC.
- 2.2.3 To describe abdominal discomfort in patients with advanced ovarian cancer treated with NAC followed by CRS with HIPEC.
- 2.2.4 To describe toxicities in patients with advanced ovarian cancer treated with NAC followed by CRS with HIPEC.
- 2.2.5 To describe the response rate in patients with advanced ovarian cancer treated with NAC followed by CRS with HIPEC.
- 2.2.6 To estimate progression-free survival (PFS) in patients with advanced ovarian cancer treated with NAC followed by CRS with HIPEC.

3.0 Patient Selection

3.1 Inclusion Criteria

- 3.1.1 Patients must have histologically or cytologically confirmed non-mucinous, epithelial stage 3 or 4 carcinoma of the ovary, fallopian tube or peritoneum.
- 3.1.2 Patients must not have received treatment for another malignancy within 3 years of enrollment.
- 3.1.3 Patients must have received at least 3 but not more than 6 cycles of carboplatin-doublet based IV neoadjuvant chemotherapy and achieved at least stable disease (radiographically confirmed) at the conclusion of this therapy.

A Phase II Trial Evaluating Quality of Life After HIPEC in Patients with Stage IIIC and IV Ovarian, Fallopian Tube or Primary Peritoneal Carcinoma
Wake Forest Baptist Comprehensive Cancer Center (WFBCCC)
CCCWU 83216

- 3.1.4 Age \geq 18 years.
- 3.1.5 ECOG performance status \leq 2.
- 3.1.6 Patients must have adequate organ and marrow function as defined below (within 30 days of registration):
 - absolute neutrophil count \geq 1,500/mcL
 - platelets \geq 75,000/mcL
 - total bilirubin \leq 1.5 mg/dL
 - creatinine clearance \geq 50 mL/min
 - AST(SGOT)/ALT(SGPT) \leq 3 X institutional upper limit of normal
 - alkaline phosphatase \leq 3 X institutional upper limit of normal
- 3.1.7 The effects of HIPEC on the developing human fetus are unknown. For this reason, and because carboplatin doublet therapy consists of pregnancy category D agents, women of child-bearing potential must agree to use adequate contraception (hormonal or barrier method of birth control; abstinence) prior to study entry and for the duration of study participation. Should a woman become pregnant or suspect she is pregnant while participating in this study, she should inform her treating physician immediately.
- 3.1.8 Ability to understand and the willingness to sign an IRB-approved informed consent document.

3.2 Exclusion Criteria

- 3.2.1 Patients may not be receiving any other investigational agents.
- 3.2.2 Patients with extra-abdominal metastatic disease.
- 3.2.3 History of allergic reactions attributed to compounds of similar chemical or biologic composition to carboplatin doublet agents.
- 3.2.4 Uncontrolled intercurrent illness including, but not limited to ongoing or active infection, symptomatic congestive heart failure, unstable angina pectoris, cardiac arrhythmia, or psychiatric illness/social situations that would limit compliance with study requirements.
- 3.2.5 Pregnant women are excluded from this study because carboplatin doublet therapy consists of pregnancy category D agents with the potential for teratogenic or abortifacient effects. Because there is an unknown but potential risk for adverse events in nursing infants secondary to treatment of the mother with carboplatin doublet therapy, breastfeeding should be discontinued.
- 3.2.6 Men are excluded from participation due to the site-specific nature of the disease being studied.

3.3 Inclusion of Women and Minorities

Women of all races and ethnicity who meet the above-described eligibility criteria are eligible for this trial. Men are excluded from participation due to the site-specific nature of the disease being studied.

The study consent form will also be provided in Spanish for Spanish-speaking participants. We plan to enroll a total of 40 individuals. Based on these study participant numbers, we expect approximately 3.5% of study participants to be Hispanic/Latino (N = 1). We plan to enroll at least 15% Black or African American (N = 6). Due to population estimates and the population in the WFBCCC catchment area we expect no or low recruitment of American Indian/Alaska Native and Asian women. Should we not meet or exceed these estimates, the PI will engage the Cancer Center Health Equity Advisory Group to discuss strategies to enhance recruitment in these target populations.

4 Registration Procedures

All patients entered on any WFBCCC trial, whether treatment, companion, or cancer control trial, **must** be linked with a protocol in EPIC within 24 hours of Informed Consent. Patients **must** be registered prior to the initiation of treatment.

You must perform the following steps in order to ensure prompt registration of your patient:

1. Complete the Eligibility Checklist (Appendix B)
2. Complete the Protocol Registration Form (Appendix A)
3. Alert the Cancer Center registrar by phone, *and then* send the signed Informed Consent Form, Eligibility Checklist and Protocol Registration Form to the registrar, either by fax or e-mail.

Contact Information:

Protocol Registrar [REDACTED]

Protocol Registrar [contact]
[REDACTED]

[REDACTED]-Friday.

4. Fax/e-mail ALL eligibility source documents with registration. Patients **will not** be registered without all required supporting documents.

Note: If labs were performed at an outside institution, provide a printout of the results. Ensure that the most recent lab values are sent.

To complete the registration process, the Registrar will:

- assign a patient study number
- register the patient on the study

5.0 Study Outcomes and Study Measures

5.1 Primary Outcome

- 5.1.1 QOL in patients with advanced ovarian cancer treated with SOC NAC followed by CRS with HIPEC as determined by the FACT-O questionnaire at 6 weeks post-treatment

5.2 Secondary Outcomes

- 5.2.1 QOL in patients with advanced ovarian cancer treated with SOC NAC followed by CRS with HIPEC as determined by the FACT-O questionnaire at 3 and 6 months post-treatment
- 5.2.2 Neurotoxicity in patients with advanced ovarian cancer treated with SOC NAC followed by CRS with HIPEC as determined by the FACT/GOG-NTX questionnaire
- 5.2.3 Abdominal discomfort in patients with advanced ovarian cancer treated with SOC NAC followed by CRS with HIPEC as determined by the FACT/GOG-AD questionnaire
- 5.2.4 Toxicities in patients with advanced ovarian cancer treated with SOC NAC followed by CRS with HIPEC (for one year post-op) as indicated by the number and severity of adverse events as defined by CTCAE v5.0
- 5.2.5 Response rates using RECIST v1.1 criteria in patients with advanced ovarian cancer treated with SOC NAC followed by CRS with HIPEC – at 3, 6, and 12 months post surgery.
- 5.2.6 PFS in patients with advanced ovarian cancer treated with SOC NAC followed by CRS with HIPEC

A Phase II Trial Evaluating Quality of Life After HIPEC in Patients with Stage IIIC and IV Ovarian, Fallopian Tube or Primary Peritoneal Carcinoma
 Wake Forest Baptist Comprehensive Cancer Center (WFBCCC)
 CCCWFU 83216

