6.0 Treatment Plan

6.1 Study-Related Interventions

	Pre-Study ^a	O.R. Day (surgery)	Follow-up Post-Treatment Visits (+/- 2 weeks)			
			6 weeks	3 Mo	6 Mo	12 Mo
Informed consent	X					
Demographics	X					
Medical history	X		X	X	X	X
Concurrent meds	X	X	X	X	X	X
Height, Weight, BSA	X		X	X	X	X
Op Note, Path Report, Perfusion Flowsheet		X				
Adverse event evaluation		X ^d	X ^d			
Physical exam and ECOG PS	X		X	X	X	X
Vital signs	X	X	X	X	X	X
B-HCG ^c	X					
CBC w/diff, plts	X			X	X	X
CMP	X			X	X	X
CA-125	X			X	X	X
CT of Abdomen, pelvis ^b	X			X	X	X
FACT-O, FACT/GOG-NTX, and FACT/GOG-AD questionnaires	X		X	X	X	

a: Pre-Study visit will occur and pre-study procedures will be completed within 28 days prior to registration.

b: CT of abdomen/pelvis as per standard-of-care.

c: B-HCG is for women of child-bearing potential only.

d: Adverse event monitoring will begin at time of surgery and will continue for six (6) consecutive weeks. AEs will be recorded in WISER at the 6 week time point.

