6.2.1.3 Postoperative Care

The patient will be transferred to the post-anesthesia care unit for aftercare and then to the intensive care unit, if needed. Early and late complications of surgery will be recorded in the patient's research chart.

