6.5 Duration of Follow Up

Tumor assessment for all lesions will be performed while patients are in the protocol follow-up phase of this study at 3, 6, and 12 months. Patients who discontinue the trial without documented tumor progression should be evaluated for extent of disease at the time of trial discontinuation.

Patients will be followed for 30 days after the HIPEC intervention is administered for adverse events monitoring.

A Phase II Trial Evaluating Quality of Life After HIPEC in Patients with Stage IIIC and IV Ovarian, Fallopian Tube or Primary Peritoneal Carcinoma
Wake Forest Baptist Comprehensive Cancer Center (WFBCCC)
CCCWU 83216

Patients will be followed for a minimum of 30 days after removal from study or until death, whichever occurs first. Patients removed from study for unacceptable adverse events will be followed until resolution or stabilization of the adverse event.

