9.2 Adverse Event Characteristics

- Adverse event monitoring will begin at the time of surgery and will continue for six (6) consecutive weeks post-op. AE's will be recorded in WISER at the six-week time point.
- CTCAE term (AE description) and grade:** The descriptions and grading scales found in the revised NCI Common Terminology Criteria for Adverse Events (CTCAE) version 5.0 will be utilized for AE reporting. All appropriate treatment areas should have access to a copy of the CTCAE version 5.0. A copy of the CTCAE version 5.0 can be downloaded from the CTEP web site (<http://ctep.cancer.gov>).
- 'Expectedness':** AEs can be 'Unexpected' or 'Expected' (see Section 7.1 above) for expedited reporting purposes only.
- Attribution** of the AE:
 - Definite – The AE is **clearly related** to the study treatment.
 - Probable – The AE is **likely related** to the study treatment.
 - Possible – The AE **may be related** to the study treatment.
 - Unlikely – The AE is **doubtfully related** to the study treatment.
 - Unrelated – The AE is **clearly NOT related** to the study treatment.

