12.0 Data Management

The Appendices contain master copies of the case report forms (CRFs) to be used for this protocol.

Note: If the patient does not have protocol therapy at surgery, it is still necessary to submit Day 0 data and the No HIPEC Follow-Up form annually.

Informed consent document

EPIC

A Phase II Trial Evaluating Quality of Life After HIPEC in Patients with Stage IIIC and IV Ovarian, Fallopian Tube or Primary Peritoneal Carcinoma
Wake Forest Baptist Comprehensive Cancer Center (WFBCCC)
CCCWFU 83216

Protocol registration Form (Appendix B)	WISER
FACT-O, FACT-GOG-NTX4, FACT/GOG-AD (Appendices H, I, J)	WISER
Follow-up form (Appendix F)	WISER
RECIST measurement form (Appendix G)	WISER
Adverse Events Log (Appendix K)	WISER

The Protocol Registration Form and signed Informed Consent Form should be completed and faxed to the WFBCCC Registrar in order to enroll and randomize participants. All other CRFs & supporting documents should be faxed to the attention of the Study Coordinator according to the following schedule:

Form	Submission Schedule
Surgery Form	Form and reports within 30 days of surgery
Perfusion Record - HIPEC Form	Form within 30 days of surgery
Adverse Event Log	Form within 7 days of completion of time period.
Follow-Up / Measurement Form	Form and supporting documents within 7 days of mo. 3, 6, and 12
FACT-O, FACT/GOG-AD, FACT/GOG-NTX	Prestudy, , Week 6, months 3 and 6 post-treatment (follow-up)

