13.2 Analysis of Secondary Objective

13.2.1 To describe QOL in patients with advanced ovarian cancer treated with SOC NAC followed by CRS with HIPEC as determined by the FACT-O questionnaire at 3 and 6 months post-treatment, the distribution of QOL at 3 and 6 months post-treatment will be examined. The descriptive statistics of QOL at 3 and 6 months post-treatment will be presented. In addition, the longitudinal data of QOL over time will be displayed graphically with individual trajectories.

13.2.2. To describe neurotoxicity at the end of study, the descriptive statistics will be presented. Since neurotoxicity is a 4-item measure from FACT/GOG-NTX4, counts and percentages will be calculated. Mean and standard deviation will be also calculated.

A Phase II Trial Evaluating Quality of Life After HIPEC in Patients with Stage IIIC and IV Ovarian, Fallopian Tube or Primary Peritoneal Carcinoma
Wake Forest Baptist Comprehensive Cancer Center (WFBCCC)
CCCWFU 83216

13.2.3. To describe abdominal discomfort at the end of study, the descriptive statistics will be presented. The abdominal discomfort is a 4-item score from FACT-GOG/AD. Counts and percentages will be calculated. Mean and standard deviation will be also calculated.

13.2.4. The toxicities will be measured by the number and severity of adverse events defined by CTCAE v5.0. Counts and percentages will be calculated for each adverse event. Mean, standard deviation, median, and interquartile range will be calculated for number of adverse events.

13.2.5. The response rate using RECIST criteria at each time point will be estimated. Counts and percentages will be calculated.

13.2.6. This secondary objective is to estimate progression free survival using survival analysis. Survival will be measured up to the time until progression, date of last contact, or death, whichever comes first. Kaplan-Meier survival curves will be used to estimate the survival probabilities. The survival probabilities for the whole sample and for the stratified groups (weekly or 3-weekly) will be calculated. The log-rank test will be used to compare the two stratified groups.

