13.6 Interim Analysis Plan

Interim reviews will be performed at 6 weeks, 3 and 6 months post-treatment to assess accrual, retention, the incidence of AEs and SAEs.

A Phase II Trial Evaluating Quality of Life After HIPEC in Patients with Stage IIIC and IV Ovarian, Fallopian Tube or Primary Peritoneal Carcinoma
Wake Forest Baptist Comprehensive Cancer Center (WFBCCC)
CCCWFU 83216

References

1. SEER Cancer Statistics Factsheets: Ovary Cancer. <http://seer.cancer.gov/statfacts/html/ovary.html>.
10. Raftery AT. Regeneration of peritoneum: a fibrinolytic study. *J Anat*. 1979;129(Pt 3):659-664.

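### Toxicity is defined over one year after surgery, but adverse events are scheduled for collection only to six weeks (30 days in one section)

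*Combined protocol and SAP*

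**What the plan says.** The current text gives three time windows for the same CTCAE v5.0 data.

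- **One year.** Secondary outcome 5.2.4 covers patients given neoadjuvant chemotherapy "followed by CRS with HIPEC (for one year post-op) as indicated by the number and severity of adverse events".
- **Six weeks.** Footnote d to the schedule in 6.1: "Adverse event monitoring will begin at time of surgery and will continue for six (6) consecutive weeks". Section 9.2 agrees: "Adverse event monitoring will begin at the time of surgery and will continue for six (6) consecutive weeks post-op". Both place recording in WISER at the six-week point. In the schedule, the adverse event row is marked on the operating day and at 6 weeks and nowhere else.
- **30 days.** Section 6.5: "Patients will be followed for 30 days after the HIPEC intervention is administered for adverse events monitoring".

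The sections that could settle the matter do not. Objective 2.2.4 gives no window. Section 13.2.4 says "The toxicities will be measured by the number and severity of adverse events defined by CTCAE v5.0" and then lists counts, percentages and summary statistics, again without a window. Section 12.0 makes the adverse event log due as follows: "Form within 7 days of completion of time period", without saying which period. Section 13.6 assumes that adverse event information is still of use at later dates: "Interim reviews will be performed at 6 weeks, 3 and 6 months post-treatment to assess accrual, retention, the incidence of AEs and SAEs".

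**The concern.** An outcome defined as the number and severity of adverse events over a period needs ascertainment over that period. Here the outcome runs to one year and the scheduled ascertainment stops at six weeks or 30 days.

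Three things follow.

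- The quantity in 5.2.4 cannot be estimated from the planned data.
- Because 13.2.4 names no window, a six-week count could be reported against an outcome labelled as one year. Readers would then take months 2 to 12 as assessed when they were not.
- The 3- and 6-month interim reviews would hold the six-week data but receive no systematically collected new events on patients past week 6.

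The gap between 30 days and six weeks is a smaller problem of its own. Staff following different sections could stop collecting 12 days apart (42 − 30), so counts might not be comparable between patients.

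**Working it through.** The plan gives no figure of its own on this point, so there is none to reproduce. The check compares the windows and then looks for any other source that could fill the gap.

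**Inputs.** Outcome window: one year, taken as 365 days (5.2.4). Collection window: 6 × 7 = 42 days (6.1 footnote d, 9.2) or 30 days (6.5). Visit allowance: ± 2 weeks (6.1). Log deadline: window plus 7 days (12.0).

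**Calendar time without scheduled collection** = (365 − window) / 365.

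| Window | Days covered | Days not covered | Share not covered |
|---|---|---|---|
| Six weeks | 42 (11.5%) | 323 | 88.5% |
| 30 days | 30 (8.2%) | 335 | 91.8% |
| Six-week visit at its latest (42 + 14) | 56 (15.3%) | 309 | 84.7% |

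The last row assumes that events are collected up to a visit held at the end of its allowance. It does not change the picture.

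**Log deadline.** 30 + 7 = day 37; 42 + 7 = day 49; 365 + 7 = day 372. The same form has three possible due dates, depending on the section followed.

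**Other sources after week 6:**

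- Section 6.2.1.3: "Early and late complications of surgery will be recorded". This covers surgical complications only, in the research chart, with no CTCAE grading and no end date.
- Sections 6.5 and 6.6: follow-up to resolution or stabilization. This applies only to patients who leave because of an adverse event, and only to that event.
- Appendix C: a general rule that all adverse events be entered in WISER. It governs data entry and schedules no assessment. The appendix's own period for expedited reporting ends 30 days after the last study treatment.
- Section 6.1: history, examination and laboratory tests at 3, 6 and 12 months, and symptom questionnaires at 3 and 6 months. Some toxicities could be derived from these, but no adverse event evaluation is marked at those visits.
- Appendix F: the follow-up form used at those visits records date and cause of death but has no adverse event item. It also asks for no further report after the first report of progression.

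None of these is a scheduled CTCAE assessment to 12 months.

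**The case against.** The best counter-argument is that the gap is one of unsystematic capture, not of absent data. The WISER entry rule in Appendix C carries no time limit, late surgical complications are charted, and patients are examined and have blood tests at 3, 6 and 12 months. On this view the real conflict is one parenthesis in 5.2.4 against two operational passages that agree on six weeks, while the 30 days in 6.5 may have been carried over from the reporting rule in Appendix C. The time shares also say nothing about how much toxicity is missed. With staggered accrual, later interim reviews would still receive new events from recently treated patients. Finally, this is one descriptive secondary outcome in a study that calls itself descriptive.

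Much of this is fair. Some late events will be recorded, and the percentages measure time only. The effect on interim reviews is limited to patients already past week 6. But incidental capture does not give the number and severity of all events over a year, which is what 5.2.4 asks for. Section 6.5 refers explicitly to adverse event monitoring, so its 30 days cannot be set aside as a reporting rule. Agreement between 6.1 and 9.2 makes the repair easier, but the outcome definition remains in conflict with them.

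**Conclusion.** The concern holds. The outcome in 5.2.4 does not match the collection in 6.1, 6.5 and 9.2, and 13.2.4 does not resolve the difference. Toxicity to six weeks can be described if the six-week window is followed. Toxicity over one year, as defined, cannot.

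Scheduled collection is absent for 88.5% of the outcome period under the six-week window and 91.8% under the 30-day window, taking a year as 365 days. How many events fall in that time is unknown, and the documents give no basis for estimating it. They also do not show which window was intended.

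This should be fixed, but it is not a threat to the main result: the primary quality-of-life comparison at 6 weeks and the sample size in 13.3 do not depend on the adverse event window.

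**What to change.** Use one adverse event window in 5.2.4, 6.1, 6.5, 9.2, 12.0 (log deadline), 13.2.4 and 13.6. There are two ways to do it.

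1. **Six weeks.** Restate 5.2.4 and 13.2.4 as toxicity to six weeks after surgery, bring 6.5 into line, and state that the adverse event part of the 3- and 6-month interim reviews covers events from that window. This is a wording change and needs no new data. Its price is a narrower claim.
2. **One year.** Keep 5.2.4, extend the window in 6.1, 6.5 and 9.2, mark adverse event evaluation at the existing 3, 6 and 12 month visits, and add an adverse event item to the follow-up form. The visits already take place, so the added work for patients still to be seen is modest data entry. Two limits need handling. The form's instruction to stop reporting after first progression would cut off toxicity data in patients who progress. Patients already past those visits could not be assessed prospectively, so the report would have to state how many have complete one-year ascertainment.

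Under either option, 13.2.4 should name the window.

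A minor related point: the schedule marks blood count and chemistry before the study and then not until 3 months. The plan should say which laboratory results feed the hematologic grades in the first six weeks.
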